
Pupillometry is a well-established, non-invasive, inexpensive indicator of LC NE activity. LC NE neuron activity increases pupil size through activation of Edinger-Westphal neurons which project to sympathetic ganglia controlling pupil diameter. Recent work has validated pupillometry as a measure of LC NE activity by simultaneously obtaining EEG, fMRI, and pupillometric data. Furthermore, the utility of pupillometry as a

biomarker of PTSD is suggested by a recent study which found increased pupil responses to threatening pictures in subjects with PTSD compared to those without PTSD. Thus, we propose to carry out a study employing pupillometry as a means of establishing the dose-response function of brexpiprazole on a key target of PTSD therapy as a means of addressing the uncertainty in dose generated by preclinical work indicating that, at least at some dosages, brexpiprazole may increase LC NE activity. We will also collect preliminary data on the dose-response effects of brexpiprazole on the clinical symptomatology of PTSD. Overall, this study is intended to provide a basis for determining the potential of brexpiprazole to be an effective therapy for PTSD. If brexpiprazole appears to be a promising therapy for this condition, our study will also serve as a basis for indicating how best to carry out clinical trials.

The broad impetus for this effort is the urgent need to develop improved therapeutics for PTSD. Treatments for this condition are extremely limited and none have demonstrated robust efficacy. It is hoped that the proposed study will serve as a key step towards evaluating whether brexpiprazole could be a much needed efficacious treatment for the many patients suffering from PTSD.

5. Design & Procedures

5.1 Subject recruitment: Participants will be recruited by running approved study specific advertisements in local newspapers and posting study flyers in the local area. We plan to consent up to 100 subjects to recruit 36 study qualifiers. Single site, double-blind, within-subjects, cross-over, dose-response study of brexpiprazole in subjects with PTSD to evaluate the effects of brexpiprazole dose on LC NE neuron activity using pupillometry and CAPS-5 ratings.

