Inclusion/Exclusion Participants will be 18-65 years of age. All subjects will be evaluated by physical examination, ECG, standard blood chemistry, hematologic labs, toxicology testing, Compliance Panel and urinalysis at baseline and end of study. Results of these studies must demonstrate a lack of clinically significant abnormalities prior to enrollment. If results are outside of the normal reference range the study physician will be consulted to assess if clinically significant. Subjects will need to satisfy DSM-5 criteria for PTSD and receive a CAPS-5 score of 33 or greater on testing for study enrollment. Subjects will need to be free of psychotropic medications or treatments that could impact results of this study as deemed by the PI for at least 1 week. If the subject's primary psychiatrist or treating primary care physician are providing the subject with psychotropic medications they will be notified and a discussion about tapering current psychotropic medications prior to study enrollment will occur.

Exclusion Criteria.

The exclusion criteria is in accordance with the package insert for brexpiprazole and can be located at https://www.accessdata.fda.gov/drugsatfda_docs/label/2015/205422s0001bl.pdf

- 1) Subjects will be excluded if they have significant medical or neurologic conditions (other than mild to moderate TBI), specifically seizures, or movement disorders,
- 2) have substance abuse within 12 months of study enrollment, substance dependence within past three months, per DSM-5 criteria (excluding caffeine and nicotine). The absence of substance use will be determined by self-report and confirmed by the results of urine toxicology at screening.
- 3) Women who are pregnant, breast-feeding, or planning to become pregnant while enrolled in this study will also be excluded.

- 4) Subjects with a history of severe drug allergy or hypersensitivity, or known hypersensitivity to the Brexpiprazole or its ingredients.
- 5) The subject has a history of tardive dyskinesia.
- 6) The subject has clinically significant extrapyramidal symptoms (EPS) including akathisia.
- 7) The subject has epilepsy or a history of seizures, except for a single seizure episode (e.g., childhood febrile seizure, post traumatic, or alcohol withdrawal).
- 8) The subject has chronic, uncontrolled, or unstable clinically relevant medical conditions Including:
 - Uncontrolled hypertension defined as blood pressure greater than 180/90

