 - Hypotension defined as a blood pressure less than 90/60
 - Moderate to severe hepatic impairment (Child-Pugh score ≥ 7)
 - Moderate, Severe or End-Stage Renal Impairment (CrCL < 60 ml/min)
 - Known CYP2D6 Poor Metabolizers
 - Heart failure NYHA Class III or IV
 - Diabetes mellitus or HbA1c greater than 5.7% (which defines pre-diabetes)
 - Hypertriglyceridemia defined as triglycerides greater than 200mg/dL
 - Low white blood cell count (below lower range of normal)
 - History of leukopenia or neutropenia
 - Arrhythmia with heart rate greater than 100bpm
 - Myocardial infarction in the past 6 months
 - Cerebrovascular accident in the past 6 months
 - Recurrent syncope
 - Seizure disorder
 - Currently receiving treatment for malignancy
 - QTc interval of greater than 450ms on electrocardiogram
- 9) The subject has a neurodegenerative disorder (Alzheimer disease, Parkinson's disease, multiple sclerosis, Huntington disease, etc.).

5.2 Study Components: There are 3 treatments (placebo, 2mg, 4mg), each for six weeks (± 3 days), separated by a 1 week (± 3 days) wash-out period. Each subject will be randomly assigned to three of the treatments. Subjects will undergo three treatments and receive 42 doses of study drug during each of the three treatment phases. Each treatment phase lasts for 6 weeks (± 3 days). For each subject, they will receive a total of 126 doses of study drug. For the brexpiprazole treatment arms, we will begin with 1mg PO q Day on Days 1 through 4 and titrate to 2mg q Day on Days 5 -7 (i.e., the 2mg brexpiprazole group will continue on 2mg daily for the remainder of the 6 weeks), and then to 4mg/day on Day 8 (i.e., this will be for the 4mg brexpiprazole group who will continue on this dose for the remainder of the 6 weeks). Irrespective of the treatment group, including placebo, subjects will be assigned three medication bottles indicated to be taken during days 1-4, days 5-7, and days 8 and up to ensure blinding during the three treatment arms. Otsuka will be providing the study medication as a bulk supply and each medication dose and placebo will look identical to each other. The study drug will be stored in a double locked medicine cabinet in the Duke Sleep Lab (Duke Clinic, 5th floor Red Zone). [name] will be creating a randomization algorithm that will be given to an unblinded study staff member to use during randomizations. The unblinded study member will prepare the study drug to be dispensed to the subjects.

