Subjects will be screened and will undergo pupil measures with rating scales on Day 1. Subject must be free of all psychotropic medications for one week before Day 1 assessment, except that prior fluoxetine treatment will require 4 weeks of abstinence, and MAOIs will require 2 weeks of abstinence. They will be randomized to study drug and issued six weeks of study medication on Day 1 to take home. A phone call will then occur for safety assessment and medication adherence at every week. They will present back to the study site on Day 42 and undergo pupil measures with rating scales. They will then undergo a one week washout period. On Day 49 they will then be given another study drug to take home with rating scales and pupil measures obtained that day. A phone call will then occur for safety assessment and medication adherence at every week. They will present back to the study site on Day 91 and undergo pupil measures with rating scales. They will then undergo a one week washout period. On Day 98 they will then be given another study drug to take home with rating scales and pupil measures obtained that day. A phone call will then occur for safety assessment and medication adherence at every week. They will present back to the study site on Day 140 and undergo pupil measures with rating scales. No more study medication will be provide on Day 140 and a final visit will be scheduled for on Day 147, one week later, for and end of study interview with labs and physical exam. At each visit, other than the final visit, subjects will complete the CAPS-5, LEC-5, MADRS, Insomnia Severity Index, Columbia Suicide Severity Rating Scale, and Clinician Assessment for Adverse Effects.

5.3 Pupilometry Procedure. We will employ Tobii Tracker Eyeglasses 2 (Stockholm, Sweden) fully mobile Eye-tracking Glasses, a non-invasive system designed to be used like a common pair of glasses (weight 75 g) in a wide range of environments, both indoors and outdoors. Pupil diameter will be recorded continuously from the each eye at a sampling rate of 50 - 100 Hz via glasses on the subject's face in a darkened room.

Primary Hypothesis: Brexpiprazole treatment will be associated with dose-dependent reduction in resting pupil diameter as a reflection of LC NE neuron target engagement in a group of subjects with PTSD.

Secondary Hypothesis: Brexpiprazole therapy will be associated with a dose-dependent decrease in CAPS-5 scores

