Tertiary Hypothesis: The pre-post treatment change in resting pupil diameter will be statistically significantly correlated with the pre-post change in CAPS-5 score.

Version: 2/3/2017

5.4 Sample Size Justification and Power Analysis: We chose an effect size of 0.3 as 6/8 prior trials of the effects of atypical antipsychotic medications on PTSD using the CAPS-5 had effect sizes larger than this and we felt that an effect of this size or larger would be clinically relevant (Liu et al., 2014). The effect-size calculation was based on the Cohen's D measure of effect size (mean difference divided by overall standard deviation). We are enrolling a sufficient number of subjects in a 3-way cross-over design study so that we could both detect this effect AND be able to detect the pupil size effect with at least 80% power. In order to address the issue of powering for 2 outcome measures we will employ Bonferoni correction to be conservative and to achieve 80% power to detect BOTH the CAPS-5 and pupil size effects at the $\alpha=0.025$ level of significance (Bonferoni correction for 2 tests dictates that we divide the $\alpha=0.05$ level by 2). We calculated that with 36 subjects we could achieve greater than 80% power to detect effects with BOTH the CAPS-5 and pupil measure at the $\alpha=0.025$ level in a one-tailed test of significance (we are only interested in whether brexpiprazole is associated with lower CAPS-5 scores and pupil diameters than placebo and will only test this hypothesis and will not test whether placebo has a greater therapeutic effect than brexpiprazole). This calculation assumed an effect size of 0.3 for both the CAPS-5 score and for the pupil measure. It should be noted that the assumption of an effect size of 0.3 for the pupil measure is highly conservative. We can estimate the effect size for the between group differences in pupil size based on our pilot work where we compared pupil size in a group of patients with depression and anxiety ($n=5$) and healthy controls ($n=5$) using the pupillometric measure to be used in the proposed study. We hypothesize that the difference in locus coeruleus norepinephrine activity (which determines pupil size in this test) in PTSD subjects will be comparable to or larger than the differences in locus coeruleus activity in patients with depression associated anxiety. The basis for this hypothesis is that the patients we studied likely have less severe arousal-system dysfunction than PTSD patients who manifest symptoms of hypervigilance which is likely to activate locus coeruleus to a comparable or greater degree and be reflected in pupillometry. The effect size for the difference in resting pupil diameter in our anxious/depressed patients and healthy controls is 2.98 based on Cohen's D. However, it is appreciated that this is derived from a very small sample of subjects who are not the identical patient population that we will be studying so we assumed that it was most conservative to assume a lower effect size than 2.98. As a result, we assume an effect size of 0.3 which is likely quite conservative for power with respect to the pupil size measure. Thus, we propose to enroll 36 subjects in our study and believe that this is conservative for having more than 80% to detect effect sizes of 0.3 for both the CAPS-5 and pupil measures with an $\alpha=0.025$, which is adjusted from 0.05 for detecting effects on 2 primary outcomes at the 0.05 level, in one-tailed tests of significance.

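### Does the crossover need its treatment orders, period term and starting visit written down before the results can be trusted?

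*Combined protocol and SAP*

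**What the plan says.** Section 5.1 describes a "Single site, double-blind, within-subjects, cross-over, dose-response study of brexpiprazole in subjects with PTSD". Section 5.2 gives three treatments (placebo, 2 mg, 4 mg), "each for six weeks (± 3 days), separated by a 1 week (± 3 days) wash-out period". On allocation it says "Each subject will be randomly assigned to three of the treatments", and that a named person "will be creating a randomization algorithm that will be given to an unblinded study staff member to use during randomizations". There are only three treatments and every subject takes all of them, so what is randomised can only be their order.

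Pupil diameter and rating scales are taken when each treatment starts (Days 1, 49 and 98) and when it ends (Days 42, 91 and 140). For the second start: "On Day 49 they will then be given another study drug to take home with rating scales and pupil measures obtained that day". For the last end: "They will present back to the study site on Day 140 and undergo pupil measures with rating scales".

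Section 5.4 gives 36 subjects, an effect of 0.3 standardised by the overall SD, a one-sided 0.025 level for each of two outcomes, and more than 80% power for both. It names no test or model. The tertiary hypothesis in section 5.3 reads "The pre-post treatment change in resting pupil diameter will be statistically significantly correlated with the pre-post change in CAPS-5 score", with no visits named.

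**The concern.** A crossover compares treatments given at different times. If PTSD symptoms or pupil size change over the 20 weeks whatever the treatment, that change enters the within-subject differences unless period is in the model. The protocol commits neither to a period term nor to equal use of the six possible orders, so an unrestricted list analysed without period is not excluded. Section 5.4 claims only a little more than 80% power, which leaves little to lose.

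The protocol also appears to name a source of drift. For subjects on psychotropics "a discussion about tapering current psychotropic medications prior to study enrollment will occur", and section 6.3 warns that symptoms may worsen, particularly around tapering.

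For the tertiary correlation, if Day 1 served as the starting visit for every period, drift shared by both outcomes could produce a correlation where no link exists.

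**Working it through.** **Inputs.** From section 5.4: N = 36, effect d = 0.3, one-sided α = 0.025. Assumed, because the protocol does not give them: the correlation ρ between a subject's end-of-period values, and a linear drift of δ SD per period. No dropout is assumed.

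**The plan's power figure.** The variance of a drug-minus-placebo difference is 2(1 − ρ), so SE = √[2(1 − ρ)/36]. At ρ = 0.8, SE = √(0.40/36) = 0.1054 and the noncentrality is 0.3/0.1054 = 2.85. Power is 79% as a paired t-test (35 df) or 80% from the crossover analysis of variance (70 df). At ρ = 0.7 and 0.9 the 70-df figures are 63% and 98%. The stated figure is therefore reachable for one outcome at ρ of about 0.8, which is used below. Power for both outcomes together needs ρ of about 0.85 if they are independent. That is a separate matter.

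**Drift with period ignored.** Under random order, two treatments lie one period apart with probability 2/3 and two apart with probability 1/3. The mean squared distance is 2/3 × 1 + 1/3 × 4 = 2, and the mean signed distance is 0. The expected estimate is unchanged, and the variance becomes 2(1 − ρ) + 2δ². At ρ = 0.8, with 70 df for the formula:

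| δ (SD per period) | Variance | Ratio to no drift | Power by formula | Simulated, simple randomisation, period ignored | Same, with period term |
|---|---|---|---|---|---|
| 0 | 0.400 | 1.00 | 80% | 80% | 79% |
| 0.1 | 0.420 | 1.05 | 78% | 78% | 79% |
| 0.25 | 0.525 | 1.31 | 69% | 69% | 78% |
| 0.5 | 0.900 | 2.25 | 46% | 47% | 79% |

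Simulated type I error with period ignored is 0.023–0.027 under simple randomisation, close to the nominal 0.025. With balanced orders it falls from 0.026 with no drift to 0.002 at δ = 0.5, which is conservative.

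**What balanced orders add.** With a period term, the SE is 0.1054 with six subjects per order and 0.1069 on average under simple randomisation. Power is 80% against 79%. If period is ignored, balance does not rescue power: 71% against 69% at δ = 0.25, and 44% against 47% at δ = 0.5.

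**Tapering as a source of drift.** The tapering discussion comes before enrolment. Section 5.2 then requires at least one week without psychotropics before Day 1 (two for MAOIs, four for fluoxetine). The first end-of-period value, on Day 42, is thus about seven weeks (7 + 41 = 48 days) after the last dose. Suppose tapering leaves a shift of 1.0 SD at Day 1 that halves every 14 days (both assumed). At Days 42, 91 and 140 it is 0.5^(41/14) = 0.131, 0.5^(90/14) = 0.012 and 0.5^(139/14) = 0.001 SD. The mean squared difference between periods is (0.119² + 0.130² + 0.011²)/3 ≈ 0.010. The variance rises from 0.400 to 0.410 and power stays at 79%, even with period ignored.

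**Analysis of change within each period.** The hypotheses speak of a reduction and a decrease, and each period has its own starting visit. If changes from those visits were compared, linear drift would be the same in every period and would cancel. Simulated power is then 49–51% at every drift from 0 to 0.5. It is lower because the starting values add noise: the variance is 4(1 − ρ) = 0.80, the SE is √(0.80/36) = 0.149 and power is about 51%. The loss owes nothing to drift.

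**Tertiary correlation.** Simulated with 36 pairs at 4 mg, no true link, equal drift in both outcomes and a two-sided 0.05 test:

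| Starting visit | δ = 0.1 | δ = 0.25 | δ = 0.5 |
|---|---|---|---|
| Each period's own (Day 1, 49 or 98) | 5% | 5% | 5% |
| Day 1 for all periods | 5% | 9% | 44% |

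**The case for a change.** The strongest case for acting is that the remedy costs almost nothing. A few sentences and a restricted list would fix the orders, model and starting visit in advance. With balanced orders the two extra degrees of freedom take less than 0.1 point of power (80.15% to 80.11%). The study makes a formal power claim and is meant to guide later trials, so calling it a pilot does not excuse the gap. A one-week washout also leaves open whether Days 49 and 98 are clean starting values.

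Much of this stands. The detail is missing, and writing it down would be tidier. But the harm requires an analyst to leave period out of a crossover, which the protocol nowhere proposes, together with a drift that it gives no reason to expect at the size needed. At 0.1 SD the loss is negligible; 0.5 SD per period, a full SD from first to last period, is extreme. Section 6.3 concerns psychiatric symptoms, and nothing in the protocol suggests a trend in pupil diameter, the subject of the primary hypothesis. The protocol gives neither the size nor the direction of any carryover, so that remains an unquantified limitation.

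**Conclusion.** No change follows. The protocol omits detail, but no rule it states gives a wrong answer. Randomised order keeps the mean shift at zero and the drug-placebo tests at or below their level, apart from simulation error. The power loss exists only under an assumed drift and an analysis that ignores period. At ρ = 0.8 it is about 2 points at 0.1 SD per period and 11 points at 0.25 SD, and the period term that analysts routinely include brings power back to 78–81%. Order balance is worth about one point. The natural reading of the tertiary hypothesis, start to end of the same period, holds false positives near 5%, and that correlation lies outside the two-outcome Bonferroni adjustment in section 5.4. All these sizes rest on assumed ρ and drift, 36 completers and one outcome at a time.

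### Each phase supplies 42 once-daily doses but may run to 45 days, so a permitted end-of-phase pupil and CAPS-5 measurement can fall after the supply has run out

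*Combined protocol and SAP*

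**What the plan says.** All the relevant text is in section 5.2 of the protocol.

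- **Supply.** Subjects "receive 42 doses of study drug during each of the three treatment phases", and over the study "they will receive a total of 126 doses of study drug". For phase 1, subjects are "issued six weeks of study medication on Day 1 to take home". Spare doses and resupply are not mentioned.
- **Frequency.** Dosing is once daily: "we will begin with 1mg PO q Day on Days 1 through 4 and titrate to 2mg q Day on Days 5 -7", with the assigned dose then continued daily to the end of the phase.
- **Packaging.** In every arm there are "three medication bottles indicated to be taken during days 1-4, days 5-7, and days 8 and up". The third bottle has no end day.
- **Duration.** "Each treatment phase lasts for 6 weeks (± 3 days", that is, 39 to 45 days.
- **Outcome visits.** For phase 1: "They will present back to the study site on Day 42 and undergo pupil measures with rating scales". Phase 2 drug is dispensed on Day 49, and then "They will present back to the study site on Day 91 and undergo pupil measures with rating scales". Phase 3 drug is dispensed on Day 98, with the measurements on Day 140. The CAPS-5 is completed at each of these visits. No window is repeated next to these days.
- **Adherence.** Weekly telephone calls cover safety and adherence. The section does not require first- or last-dose dates to be recorded, and it sets no limit on the time from last dose to measurement.

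**The concern.** The dose count fits only a phase of exactly 42 days, while the plan allows a phase to be up to 3 days longer. The visit that closes the phase supplies the treatment value for both powered measures, pupil diameter and CAPS-5. The primary hypothesis treats pupil diameter as a marker of target engagement, which is a question about subjects who are on drug.

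If some end-of-phase values are taken after the drug has run out, active-arm values could move toward placebo, which works against the dose-response the trial seeks. Time since last dose could also differ between phases. That is unwelcome in a crossover, where the comparisons are made within subject across phases.

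**Working it through.** **Inputs (section 5.2).** 42 doses per phase; one dose a day; phase length 42 ± 3 days; dispensing on Days 1, 49 and 98; end-of-phase visits on Days 42, 91 and 140. The plan does not say whether the first dose is taken on the dispensing day or the next day, so both are shown. Full adherence is assumed, and the visit is assumed to move with the ± 3 day phase window.

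**The plan's own total.** 3 × 42 = 126, as stated. Across the three bottles, 4 + 3 + 35 = 42. The total therefore contains no extra doses.

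**Doses needed by phase length, at one a day.**
- 39 days: 39 doses, 3 left over.
- 42 days: 42 doses, an exact match.
- 45 days: 45 doses, 3 short. Over three such phases, 3 × 45 = 135 against 126.

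**Days from last supplied dose to visit.** Last dose day = first dose day + 41. Gap = visit day − last dose day. A negative gap means supply remains.

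| Phase | First dose | Last supplied dose | Gap at nominal visit | Gap at latest visit (+3) |
|---|---|---|---|---|
| 1 | Day 1 | Day 42 | 42 − 42 = 0 | 45 − 42 = 3 |
| 1 | Day 2 | Day 43 | 42 − 43 = −1 | 45 − 43 = 2 |
| 2 | Day 49 | Day 90 | 91 − 90 = 1 | 94 − 90 = 4 |
| 2 | Day 50 | Day 91 | 91 − 91 = 0 | 94 − 91 = 3 |
| 3 | Day 98 | Day 139 | 140 − 139 = 1 | 143 − 139 = 4 |
| 3 | Day 99 | Day 140 | 140 − 140 = 0 | 143 − 140 = 3 |

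**Which window days matter.** With once-daily dosing, a measurement one day after the last dose is an ordinary end-of-interval value, much like one taken just before that day's dose. Only gaps of 2 days or more exceed one dosing interval. In phase 1 with the first dose on Day 1, the window is Days 39 to 45 and the days with a gap above 1 are Days 44 and 45, which is 2 of 7.

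At the early end of the window no phase has a shortfall; 2 to 4 doses remain.

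**The case against.** The strongest reply is that the window belongs to the phase, not the visit. The ± 3 days is attached to treatment length, while the visits are given as fixed days. On that reading 42 and 126 are nominal counts, the open-ended third bottle could cover a longer phase, and unblinded staff prepare it from bulk supply. If visits are held exactly on Days 42, 91 and 140, the gap is never more than one day.

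Part of this stands: the visit window is inferred. But the end-of-phase visit closes the phase and the washout follows it, and no other visit window is given. The bottle label does not add doses to a stated 42 per phase and 126 in total. Weekly adherence calls do not add any either. Missed doses would stretch the supply, but a schedule should not depend on non-adherence to work.

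Three stronger readings are tempting, and the documents do not support them.

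- *On-time visits in phases 2 and 3 are off drug.* The one-day gap arises only if the first dose is taken on the dispensing day, and even then it is one ordinary dosing interval. If dosing starts the next day, the gap is 0.
- *Every visit after day 42 of a phase is a run-out.* A visit on day 43 is within one dosing interval of a dose taken on day 42.
- *A specific loss of effect or power follows.* That would need a half-life, a link between drug level and each outcome, a distribution of visit days and a within-subject correlation. The documents give none of these. Visits may cluster near the nominal day, and CAPS-5 need not track drug level closely.

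**Conclusion.** The concern holds as an internal inconsistency with a plausible, unquantified effect on the outcome. The dose count, the maximum phase length and once-daily dosing cannot all be met in a phase longer than 42 days; the shortfall reaches 3 doses.

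If the visit moves with the phase window and adherence is full, the latest permitted measurement falls this long after the last supplied dose:

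- Phase 1: 3 days with the first dose on Day 1, or 2 days with the first dose on Day 2.
- Phases 2 and 3: 4 days with the first dose on the dispensing day, or 3 days with the first dose the next day.

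The direction of any effect, active-arm values pulled toward placebo, is reasonable to expect. Its size cannot be derived from the documents, and a bias has not been shown.

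**What to change.** 1. Reconcile the 42-dose supply, the ± 3 day phase length and the Day 42, 91 and 140 visits, so that no permitted end-of-phase measurement falls after supply has run out. Which figure changes is for the sponsor and investigator. The text should also say whether the window applies to the visit and on which day the first dose of each phase is taken.
2. Record the first- and last-dose dates in each phase.
3. Pre-specify a sensitivity analysis of pupil diameter and CAPS-5 by time since last dose, applying the same definition in the placebo phase. Simply dropping every value taken after the last supplied dose could cost many values in a 36-subject crossover, so the cut-off should be chosen with the dosing interval in mind.

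The cost is a short amendment, one or two case-report fields, one extra analysis, and either slightly more supply or a tighter window. Recording dates does not recover an on-drug measurement already missed, so the first step matters most.

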A Pilot Dose-Response Biomarker Study of Brexpiprazole Treatment in PTSD
(Terminated)

NCT02934932

Document Date: February 3, 2017

1. Title: A Pilot Dose-Response Biomarker Study of Brexpiprazole Treatment in PTSD

2. Purpose of the Study: To determine if brexpiprazole treatment will be associated with a dose-dependent reduction in resting pupil diameter as a reflection of locus coeruleus (LC) norepinephrine (NE) neuron target engagement in a group of subjects with PTSD. To determine if brexpiprazole therapy will also be associated with a dose-dependent decrease in the clinician administered PTSD scale (CAPS-5) scores. To determine if the pre-post treatment change in resting pupil diameter will be statistically significantly correlated with the pre-post change in CAPS-5 score.

3. Primary Objectives:

Specific Aim 1: Evaluate the effects of two doses of brexpiprazole on locus coeruleus (LC) norepinephrine (NE) neuron activity.

Specific Aim 2: Determine the effect of brexpiprazole therapy on PTSD symptom severity.

Specific Aim 3: 1) Evaluate whether depression severity improves with treatment and assess how this relates to PTSD response; 2) Specifically evaluate the degree to which treatment improves nightmares; 3) Evaluate the effects of treatment on sleep disturbance.

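### The hypotheses claim a dose-dependent reduction, but the only treatment test stated is brexpiprazole below placebo, which cannot support that conclusion

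*Combined protocol and SAP*

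**What the plan says.** Section 2 gives the purpose as "To determine if brexpiprazole treatment will be associated with a dose-dependent reduction in resting pupil diameter", and says the same of CAPS-5. Specific Aim 1 in Section 3 is to "Evaluate the effects of two doses of brexpiprazole on locus coeruleus (LC) norepinephrine (NE) neuron activity". The primary hypothesis in 5.3 is "Brexpiprazole treatment will be associated with dose-dependent reduction in resting pupil diameter as a reflection of LC NE neuron target engagement"; the secondary hypothesis is a dose-dependent decrease in CAPS-5. Under 5.2 every subject receives placebo, 2 mg and 4 mg in a crossover.

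The treatment comparison appears only in 5.4, where interest is confined to whether "brexpiprazole is associated with lower CAPS-5 scores and pupil diameters than placebo and will only test this hypothesis". The level is 0.025 one-sided, "which is adjusted from 0.05 for detecting effects on 2 primary outcomes at the 0.05 level, in one-tailed tests of significance". The effect size of 0.3 is Cohen's d, defined as "mean difference divided by overall standard deviation". With 36 subjects, 5.4 states more than 80% power for both outcomes. No other section describes an analysis of treatment effects; the tertiary hypothesis, a correlation between pupil and CAPS-5 changes, compares neither treatments nor doses.

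**The concern.** The hypothesis is about how the effect changes with dose; the test is about drug against placebo. The second can succeed when the first is false, for example when both doses work equally well. Section 4 makes this more than a formality: it says preclinical data suggest that some doses may increase locus coeruleus activity, and it presents the study as a way to settle the dose question before larger trials. If no between-dose contrast is fixed in advance, a dose-dependence conclusion risks resting on a comparison chosen after the data are seen.

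Two related points in 5.4 are also open. CAPS-5 is secondary in 5.3 but one of two primary outcomes in 5.4. And the divisor of 2 ("Bonferoni correction for 2 tests dictates that we divide the" 0.05 level by two) counts outcomes, not doses, so it is unclear which contrast the 0.025 and the power refer to.

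**Working it through.** **Inputs.** From 5.4: n = 36, d = 0.3 in units of the overall SD, one-sided 0.025. From 5.2: three treatments per subject. Assumed, because the documents give none: within-subject correlation ρ, equal between periods, mainly 0.5 and 0.8, with higher values where shown. Also assumed: one value per period and no dropout.

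**Formula.** A difference between two treatments has SE = √(2(1−ρ)/n) in overall-SD units. A model with subject, period and treatment leaves (36−1)(3−1) − 2 = 68 df. Power comes from the noncentral t with noncentrality (effect)/SE.
- ρ = 0.5: SE = √(1.0/36) = 0.167; noncentrality 0.3/0.167 = 1.80.
- ρ = 0.8: SE = √(0.4/36) = 0.105; noncentrality 0.3/0.105 = 2.85.

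**1. The plan's own power.** It cannot be reproduced, because neither ρ nor the contrast is stated. For one dose against placebo at 0.025:

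| ρ | 0.5 | 0.7 | 0.8 | 0.85 | 0.9 |
|---|---|---|---|---|---|
| Power | 43% | 63% | 80% | 90% | 98% |

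Reaching 80% needs ρ of about 0.80. For 80% on both outcomes jointly, if independent, each needs √0.8 = 89.4%, hence ρ of about 0.85. If the two doses were averaged against placebo, the corresponding values would be about 0.73 and 0.80.

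**2. Flat response, both doses −0.3 SD.** There is no dose-dependence between 2 mg and 4 mg. Yet 4 mg versus placebo rejects in 43% (ρ = 0.5) or 80% (ρ = 0.8) of trials. A linear trend gives no protection: over 0, 2 and 4 mg its weights are −1, 0, +1, so it is the 4 mg-placebo test. The 4 mg-2 mg contrast rejects in 2.5%, as it should.

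**3. Alpha.** If each dose were tested against placebo at 0.025 on one outcome, the familywise error would be 4.5%. On both outcomes (four tests) it would be 8.9% to 7.0% for a correlation between outcomes of 0 to 0.8, against the 5% intended. Which case applies depends on choices the plan does not make.

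**4. A rule for claiming dose-dependence** (simulation, 1 million draws, alpha 0.025 per outcome). The rule requires 4 mg below placebo under Holm, 4 mg below 2 mg at 0.025, and a 2 mg estimate not above placebo.

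| True reduction, placebo/2 mg/4 mg (SD) | ρ = 0.5 | ρ = 0.8 | ρ = 0.9 |
|---|---|---|---|
| 0/0.15/0.30 | 7 to 8% | 23% | 49% |
| 0/0.30/0.60 | about 40% | 80% | 98% |

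Under the flat response of step 2, the first two conditions alone give a false claim in 2.0% (ρ = 0.5) or 2.4% (ρ = 0.8), and a third condition can only lower this. The third condition matters when 2 mg raises and 4 mg lowers pupil size by 0.3 SD. If it asked only that the 2 mg-placebo 95% CI not lie wholly above zero, the claim would still be made in 24% (ρ = 0.5) or 18% (ρ = 0.8) of trials. Asking that the 2 mg estimate not exceed placebo cuts this to 2.5% or 0.2%.

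**5. Dose-placebo tests under Holm.** The first step at 0.0125 and 0.3 SD has power 32%, 71%, 84% and 96% at ρ = 0.5, 0.8, 0.85 and 0.9; 80% is reached at about 0.84.

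**The case against.** The best defence is that the sentence in 5.4 explains why the tests are one-sided, as its ending shows: "will only test this hypothesis and will not test whether placebo has a greater therapeutic effect than brexpiprazole". It need not be a full list of contrasts. This is a pilot, every subject receives all three treatments, and effects by dose can be estimated whatever 5.4 says. Dose-dependence also has several defensible definitions, and a contrast could still be fixed before unblinding.

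Much of this stands, and it limits what may be inferred:
- A reader might infer that the plan pools the two doses. No passage says so.
- A reader might infer that type I error is inflated. That holds only if each dose is tested on both outcomes at 0.025, which the plan does not state.
- A reader might infer that the power statement is wrong. It is unverifiable: a correlation of about 0.80 to 0.85 or more would support it for a single dose-placebo test per outcome, and the documents neither give nor exclude that.
- A reader might infer that the trial cannot address dose. The crossover data can; the gap is in the plan.

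What the defence does not supply is any between-dose comparison. Pilot status does not remove the need for one, since the plan sets an alpha, corrects it and claims power for a hypothesis worded as dose-dependent.

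**Conclusion.** The point holds. The stated test does not answer the stated primary and secondary hypotheses, and a significant drug-placebo or linear-trend result would not show dose-dependence: with two equally effective doses it would occur in 43% to 80% of trials at correlations of 0.5 to 0.8. The mismatch itself needs no calculation. The percentages rest on the assumed correlation, one value per period (although 5.2 also schedules measurements at the start of each period) and no dropout. The conflicting label for CAPS-5 leaves the alpha family unsettled, and the power above 80% cannot be checked without a named contrast and a correlation. This should be fixed before analysis; it does not undermine the design.

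**What to change.** In 5.3 and 5.4:
1. Analyse each outcome in one crossover model with subject, period and a three-level treatment factor, without pooling the doses.
2. Give CAPS-5 one label. The smaller change is co-primary at one-sided 0.025 per outcome, which 5.4 already uses.
3. Name 2 mg-placebo and 4 mg-placebo as the tests, with a stated multiplicity method (for example Holm) within each outcome's alpha. Report 2 mg-placebo, 4 mg-placebo and 4 mg-2 mg with two-sided 95% CIs, noting that these are unadjusted and may not match the adjusted tests.
4. Do not conclude a dose-dependent reduction from a drug-placebo or linear-trend result alone. Require 4 mg below placebo under item 3, 4 mg below 2 mg at that outcome's alpha, and a 2 mg estimate not above placebo. Otherwise report the effects by dose as estimates.
5. Restate the power for each named contrast with the assumed correlation, number of values per period and dropout.

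The cost is wording and a less favourable, conditional power statement; no visits or data are added and n stays at 36. Power for the dose-dependence claim is low for a shallow gradient (7 to 8% up to 23% for 0/0.15/0.30 SD at correlations of 0.5 to 0.8). 5.4 should therefore say that failing to make the claim is not evidence of no dose effect and that the intervals must be read instead.
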